## **4.2.2 Rationale for Endpoints**

### **4.2.2.1 Outcome Measures Rationale**

As in the protocol for the initial 104-week trial, the primary outcome measure is the change from Baseline in the Clinical Dementia Rating Scale Sum of Boxes (CDR-SB) score at 130 weeks. The CDR-SB is highly relevant clinically and has been shown to worsen over time in this patient population.

Progression to probable AD dementia will be included in the long term trial as an exploratory objective. This study will use both NINCDS ARDRA and Diagnostic and Statistical Manual of Mental Disorders, 4th Edition, Text Revision (DSM-IV-TR) criteria to define probable AD dementia. Unlike the initial 104-week trial, cases of progression in the long term trial

will not be reviewed by an adjudication committee; therefore, the final decision on progression will be the opinion of the investigator or qualified designee. The progression endpoint will provide useful information for patients and physicians for understanding the effects of MK-8931.

Other clinical measures include the following: a) the composite cognition score (based on the mean of the three domain z-scores from tests of episodic memory, working memory/executive function, and attention/psychomotor speed) and b) the Alzheimer's Disease Cooperative Study Activities of Daily Living Inventory (ADCS ADLMCI) (mild cognitive impairment [MCI] version) score. Previously conducted trials have demonstrated that cognition and function are relevant dimensions of clinical progression in this patient population. Regarding cognition, prior studies of MCI have used some version of the Alzheimer's Disease Assessment Scale Cognitive subscale (ADAS-Cog). Because of the well-known issue with sensitivity of the ADAS-Cog, many studies have also included additional, standard cognitive tests. Several methods have been proposed to combine the ADAS-Cog with the additional tests to generate a composite cognition score. While intensive ongoing research may clarify the optimal approach, this protocol will calculate the average z-score of three cognitive domains thought to be involved in prodromal AD based on modeling suggesting this is superior to the ADAS-Cog alone.

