Three supportive analyses will be conducted on the primary efficacy endpoint. These analyses will be conducted to assess the effect of 1) missing data using a pattern-mixture model “tipping-point” approach, which is intended to provide a measure of robustness in the (unobservable) event that a larger-than-expected proportion of the missing data be missing-not-at-random (MNAR) 2) the use of off-regimen data after the subject has permanently discontinued trial medication or after the subject has initiated AChEIs and 3) analysis using the cLDA model on the MFAS population.

For the first sensitivity analyses (tipping-point), the model-based estimates of the mean treatment difference on the change scores, along with the corresponding confidence intervals and p-values will be provided for a range of  $c$  values which have been subtracted from the values imputed for the active arms (see Section 8.2.7.5 for more details). Of specific interest is the smallest  $c$  value that, for a given endpoint, transforms a “statistically significant” result to a “non-statistically significant” result (per the pre-defined  $\alpha$ -level used in the initial 104-week trial).

For the second sensitivity analysis (excluding observations obtained after study medication discontinuation or after the initiation of AChEIs), the model-based estimates of the mean treatment difference on the change scores, along with the corresponding confidence intervals and p-values will be provided.

For the third sensitivity analysis (cLDA model on the MFAS population), the analysis of the primary efficacy endpoint will be conducted using a constrained longitudinal data analysis (cLDA) method proposed by Liang and Zeger [28]. This model assumes a common mean across treatment groups at baseline and a different mean for each treatment at each of the post-baseline time points. The response vector consists of baseline and the values observed at each post-baseline time point. The model-based estimates of the mean treatment difference on the change scores, along with the corresponding confidence intervals and p-values will be provided as obtained using the cLDA model, with all of the same covariates that were included in the primary model (now excluding the terms for baseline and baseline-by-time interaction). An unstructured covariance model will be used.

Table 6 Analysis Strategy for Primary Endpoints

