### 8.2.7.2 Exploratory Efficacy Analyses

One exploratory endpoint is the time to progression to probable AD dementia as determined by investigator-diagnosis (noting that the formal adjudication process utilized in the initial 104-week study, will not be utilized in the long-term safety study). All available data from the initial 104-week trial will be utilized in the analysis. A Cox proportional hazard model adjusting for APOE4 genotype (APOE4 positive, APOE4 negative), gender, geographic region, and the use of acetylcholinesterase inhibitors at screening (Use, Do Not Use) as categorical terms, with age and baseline MMSE score as continuous covariates will be used to compare the hazard functions of the 40 mg/40 mg arm to the Pbo/40 mg arm, as well as to compute the hazard ratios and the corresponding confidence intervals (CIs). Subjects who reach the maximum treatment duration will be considered as completers and will be censored at that timepoint.

The 12 mg/12 mg arm will be compared to the Pbo/40 mg arm in a similar fashion.

If the analysis model fails to converge due to the presence of too many factors in the model (i.e., empty cells), then factors will be removed one at a time until the model does converge. Factors will be removed in the following order: geographic region, gender, use of acetylcholinesterase inhibitors at screening, and APOE4 genotype.

For all other continuous exploratory endpoints, the same model that is used for the primary endpoint will be used as were specified in Section 8.2.3.1.

No sensitivity analyses will be conducted on any of the exploratory endpoints.

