- b. Applying parametric regression to the monotone-missing datasets, impute the missing values in a stepwise fashion starting with the first postdose timepoint. This will be accomplished for each treatment group using “PROC MI” within SAS 9.3 utilizing the option “monotone reg”, in conjunction with all of the covariates (excluding treatment) included in the primary analysis model. The random seed will be set equal to 8931019. This step will generate  $m$  complete datasets.
- c. To implement the tipping-point aspect of the procedure, subtract a constant  $c$  from each of the imputed values of the active arms (to the detriment of active).
- d. Analyze each of the post-imputation complete datasets using the primary model, obtaining point estimates for the mean of interest (e.g., change-from-baseline treatment difference at 104 weeks) and the associated variance.

Using “proc mianalyze” within SAS 9.3, the  $m=50$  means and variances from the  $m$  analyses will be combined to obtain the final test statistic and p-value [29]. The final test statistic  $\bar{Q} / (T^{(1/2)})$  is approximately distributed as  $t_v$ , where  $\bar{Q}$  is the sample mean of the  $m$  mean estimates,  $T = \bar{U} + (m+1) (B/m)$ ,  $\bar{U}$  is the sample mean of the  $m$  variance estimates, and  $B$  is the sample variance of the  $m$  mean estimates. The degrees of freedom,  $v$ , will be computed as follows [33],  $v = [(v_1)^{-1} + (v_2)^{-1}]^{-1}$ , where  $v_1 = (m-1) [1 + (\bar{U}/(1+m^{-1}) B)]^2$  and  $v_2 = (1-\gamma) v_0 (v_0 + 1) / (v_0 + 3)$ , with  $\gamma = (1+m^{-1}) B / T$  and where  $v_0$  represents the complete-data degrees of freedom.

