This procedure will be repeated (using the same  $m$  imputed datasets) until the smallest  $c$  is found such that the “significant” result turns “non-significant” (i.e.,  $p \geq 0.02495$ ). This tipping point value  $c$  provides a measure of robustness of the primary result. A relatively large value of  $c$  implies better robustness of the primary analysis against the impact of missing data in the study. It is noted that when  $c=0$  the tipping point analysis described above corresponds to an analysis conducted under the assumption that the missing data are MAR. For values of  $c$  larger than 0, the tipping point analyses do not assume that the missing values follow a MAR mechanism. In fact, the analysis is based on a special MNAR mechanism in which all missing data in the active arm are assumed to have a worse response

by a constant amount of  $c$  than the values would have had under MAR, while the missing data in the control group are assumed to be the same as that obtained under MAR.

It may be necessary to adjust  $c$ , in order to calibrate between the two analysis approaches (ANCOVA vs. MI), should a value of  $c=0$  yield a different p-value than is produced from the primary ANCOVA analysis model. This will be accomplished by subtracting the calibration value  $c_{prim}$  from  $c$ , where  $c_{prim}$  is the offset to be applied to the active arm, per the above MI approach, that will yield the same p-value as produced by the primary ANCOVA analysis.

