### 8.2.11 Sample Size and Power Calculations

#### 8.2.11.1 Sample Size and Power for Efficacy Analyses

##### 8.2.11.1.1 Parameter Estimates

Parameter estimates for the primary endpoint were obtained from the Alzheimer's Disease Neuroimaging Initiative (ADNI). Extrapolations out to 30 months (Week 130) were performed on the 24-month (Week 104) parameter assumptions used in the initial 104-week trial and these extrapolations are presented below in [Table 8](#).

Table 8 Parameter Assumptions for CDR-SB

Endpoint	Baseline SD	30m SD	30m CFB Mean (130-Week Placebo/ MK-8931 40 mg Progression Rate)	Corr(Base, 30m)
CDR-SB	0.86	3.05	2.13	0.359

Based on N=151 subjects from ADNI, Late MCIs with either CSF+ ( $\tau\text{au}/\text{ab142} \geq 0.39$ ) or PET+ ( $\text{pib} > 1.6$ ), and MMSE  $\geq 24$ .

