### 8.2.11.1.2 Power Calculations

Power calculations for the change-from-baseline treatment difference at 30 months (Week 130) were performed (via simulation) for CDR-SB even though there are no formal hypotheses for the endpoint in the long term trial. As shown in Table 9 the hypothesis is underpowered at Week 130, both marginally and when applying an informal sequential testing approach. Specifically, it is possible that formal statistical significance may be observed in the initial 104 week trial (under the prespecified multiplicity approach), while nominal marginal significance (ie, p-value < 0.02495) fails to be observed at Week 130, even if the true underlying effect of MK-8931 continues to increase. This is due to the assumed increased variance and dropout rate over time, with 90% of subjects who complete the base study assumed to continue on into the extension.

Table 9 Power Calculations (MK-8931 40 mg / MK-8931 40 mg vs. Placebo / MK-8931 40 mg)

Marginal Probability †	(%)
CDR-SB at Week 130	73.9
Sequential Probability	
Success ‡ for CDR-SB at Week 104 and CDR-SB at Week 130	73.4
Conditional Probability	
Success ‡ for CDR-SB at Week 130 given success on CDR-SB at Week 104	76.1
† Marginal power calculations at Week 130 do not require success at Week 104. ‡ 40 mg dose only Calculations are based on N=1350 randomized (450 subjects/arm) incorporating the assumed dropout rate of 25% at Week 104 and 37% at Week 130 ( $\alpha = 0.02495$ ).	

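### The tipping-point analysis subtracts c from the active arms' imputed CDR-SB changes, which favours active, although the plan says the shift should penalise active

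*Combined protocol and SAP*

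**What the plan says.** Section 8.2.7.5 sets out a multiple-imputation procedure with m = 50. Step c shifts the imputed values by subtracting c "from each of the imputed values of the active arms (to the detriment of active"). Section 8.2.7.1 describes the same operation, reporting results for a range of c values "which have been subtracted from the values imputed for the active arms".

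Section 8.2.7.5 then explains what is intended. For c above zero, "all missing data in the active arm are assumed to have a worse response" by the amount c, while the control group stays at its missing-at-random values. The search is for the smallest c at which a significant result loses significance (p of 0.02495 or more), and a larger c is read as greater robustness.

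The direction of the scale can be read from the plan itself. Section 4.2.2.1 says the CDR-SB "has been shown to worsen over time in this patient population". Table 8 gives a value of 2.13 under the column headed "30m CFB Mean (130-Week Placebo/ MK-8931 40 mg Progression Rate"), so a positive change is worsening.

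The procedure has one target. Table 6 lists it for CDR-SB at Week 130 only, and section 8.2.7.2 states: "No sensitivity analyses will be conducted on any of the exploratory endpoints".

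**The concern.** The operation and its stated purpose point in opposite directions. If a higher CDR-SB change is worse, lowering the active arms' imputed changes makes active look better. A programmer who follows the arithmetic and one who follows the explanation will write programs with opposite results.

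The risk lies in the literal version. A significant benefit would move further from the threshold as c grows and would never tip. Since the plan equates a large tipping value with robustness, failure to tip could be reported as strong reassurance when no stress test had taken place. Only a significant result against active would tip.

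Table 6 has no other analysis of the primary endpoint that departs from missing-at-random. Missing data are not a side issue either: Table 9 uses an "assumed dropout rate of 25% at Week 104 and 37% at Week 130".

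**Working it through.** **Direction.** Let D be the active-minus-control difference in mean CDR-SB change at Week 130, so a negative D favours active. If a share f of the active arm is imputed and each imputed value is shifted by c, the active mean moves by f × c. With f = 0.37:

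- subtracting c: D becomes D - 0.37c, further in favour of active;
- adding c: D becomes D + 0.37c, towards the null.

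The sign of this result needs no assumed effect size.

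**Could another endpoint justify subtraction?** It would be right on a scale where lower is worse. Table 6 and section 8.2.7.2 leave only CDR-SB. Nothing in the plan reverses the score, and c is described as larger than zero.

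**Inputs for a numerical illustration**

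- 450 per arm, 37% missing, alpha 0.02495 (Table 9). Alpha is taken as two-sided because section 8.2.10 pairs it with 97.51% confidence intervals, so z = 2.242.
- Week 130 SD 3.05 and baseline correlation 0.359 (Table 8). Baseline-adjusted SD = 3.05 × √(1 - 0.359²) = 2.847.
- m = 50 (section 8.2.7.5).
- Assumed D = -0.69. The plan gives no Week 130 difference, so Table 9's 73.9% power cannot be reproduced forwards. Solving backwards with 450 × 0.63 = 283.5 observed per arm: SE = 2.847 × √(2/283.5) = 0.239, and (2.242 + 0.640) × 0.239 = 0.689. Using SD 3.05 gives 0.74; a one-sided alpha gives 0.62.

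**Variance.** Under Rubin's rules at c = 0:

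T = 2 × 2.847² × [1/450 + 1.02 × (1/283.5 - 1/450)] = 0.0576, so SE = 0.240.

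The shift adds 0.37 × 0.63 × c²/450 to the active arm's within-imputation variance. At c = 0.5 that is 0.00013, and SE is still 0.240.

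**Results for D = -0.69 (normal approximation)**

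| c | D, c subtracted | p | D, c added | p |
|---|---|---|---|---|
| 0 | -0.690 | 0.004 | -0.690 | 0.004 |
| 0.5 | -0.875 | 0.0003 | -0.505 | 0.036 |
| 1 | -1.060 | 0.00001 | -0.320 | 0.18 |

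- Added: the tip is at (0.69 - 2.242 × 0.240)/0.37 = 0.41.
- Subtracted: \|z\| starts at 2.88 and, checked up to c = 500, never falls below that value. The added variance does not rescue it, because \|z\| tends to 0.37/√(0.37 × 0.63/450), about 16. No tipping point exists.
- If active were worse by 0.69, literal subtraction would tip at about 0.4.

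**Range of the corrected tipping value**

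| Assumption changed | Tipping c |
|---|---|
| D = -0.54 | under 0.05 |
| D = -0.62 | about 0.2 |
| D = -0.74 | about 0.5 |
| D = -0.80 | about 0.7 |
| D = -0.69, 25% missing | about 0.8 |
| D = -0.69, 45% missing | about 0.25 |
| D = -0.69, SD 3.05 | 0.31 |

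A simulation with 60 datasets per assumed difference, regression imputation by arm and the plan's degrees-of-freedom formula gave a median tip of 0.40 (range 0.15 to 0.60) for -0.69 and 0.70 (0.50 to 1.0) for -0.80. Median p for -0.69 was 0.005 at c = 0, 0.0004 with 0.5 subtracted and 0.041 with 0.5 added.

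**The case against.** The best defence is that the intent is plain. The detriment to active is stated in the same sentence as the subtraction, the explanation that follows confirms it, and the search is for a c that removes significance. A program that helps active would breach step c as well as follow it. The error would probably also show itself: the search would not end for a significant benefit, and the required output over a range of c would show the effect growing. Finally, the analysis is supportive, there are no formal hypotheses, and the plan calls Week 130 underpowered.

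Most of this is fair and limits the weight of the point. It does not remove it. The operative instruction has the wrong sign in two sections, and detection depends on someone questioning output that matches the written step. If the sign is settled only after unblinding, the choice is made with the results in view.

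The numbers also invite an objection. The -0.69 is back-solved, not stated. The 37% is assumed dropout among randomized subjects, not a demonstrated missing share in the full analysis set. The calculation takes equal missingness in both arms and a single-visit model. That stands: the tipping values are illustrations, and only the direction is established.

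**Conclusion.** The concern holds. As written, the shift improves the active arms on CDR-SB, contrary to the plan's own description, and no other planned use of the procedure makes subtraction correct. Followed literally, the only missing-not-at-random check on the primary endpoint cannot tip a significant benefit at any c above zero. The direction rests only on Table 8 and section 4.2.2.1.

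The size depends on an assumed Week 130 difference. For values from -0.54 to -0.80 with 37% missing, the correctly signed analysis tips somewhere between under 0.05 and about 0.7 CDR-SB points, where the literal version reports no tip. This should be fixed, but it is confined to a supportive analysis. The primary estimate, its interval and the power calculations do not change.

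**What to change.** In section 8.2.7.1 and in step c of section 8.2.7.5, replace the subtraction with: *add c to the imputed CDR-SB change scores of the 40/40 and 12/12 arms, so that c > 0 worsens them*.

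The calibration formula, c minus c_prim, can stay. Section 8.2.7.5 defines c_prim through the same imputation procedure, so it takes the corrected sign once step c is corrected.

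As a minor tidy-up, the example in step d still cites a "change-from-baseline treatment difference at 104 weeks"; it should read 130 weeks, the endpoint in Table 6.

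The cost is two phrases in the SAP and, if already coded literally, one sign in the program. Data collection and the primary analysis are untouched. The change should be made before unblinding.

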## **8.2.4 Analysis Populations**

### **8.2.4.1 Efficacy Analysis Populations**

The Full Analysis Set (FAS) population will serve as the primary population for the analysis of efficacy data in this study. The FAS population for a given endpoint consists of all randomized subjects who:

- receive at least one dose of study treatment,
- have both 1) a baseline measurement for the analysis endpoint and 2) at least one within-analysis-window ( $\pm 6$  weeks) post-dose, post-randomization observation for the analysis endpoint, and
- are PET positive.

All available observations from the initial 104-week trial will be included in the relevant model-based FAS analyses. Observations from the long term trial will be included according to the principles outlined above, with the following additional requirement: the subject must have taken at least one dose of study medication within the 28 days preceding the 104-week visit and within the 28 days following the 104-week visit.

The Modified Full Analysis Set (MFAS) population will be utilized for sensitivity analyses and is defined identically to the FAS population with one exception: patients will only be required to have either 1) a baseline measurement for the analysis endpoint or 2) at least one within-analysis-window ( $\pm 6$  weeks) post-dose, post-randomization observation for the analysis endpoint, but not necessarily both.

The MFAS population will be utilized to conduct sensitivity analyses in this study for the primary endpoint (CDR-SB 30-Month CFB).

Though no Per-Protocol analyses are planned, a list of protocol violations/violators will be maintained. The final determination on protocol violations will be made prior to the final unblinding of the database and will be documented in a separate memo.

Subjects will be included in the treatment group to which they are randomized for the analysis of efficacy data using the FAS population.

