Endpoint/Variable (Description, Time Point)	Primary vs. Supportive Approach	Statistical Method	Analysis Population	Missing Data Approach
Primary Endpoint				
CFB in CDR-SB scores at 130 Weeks	P	Longitudinal ANCOVA	FAS	Model-based
	S	Longitudinal ANCOVA	FAS	Pattern-Mixture Model (Tipping Point)
	S	Longitudinal ANCOVA (Exclude data collected after the introduction of AChEIs and/or study medication discontinuation)	FAS	Model-based
	S	cLDA	MFAS	Model-Based
AChEIs= acetylcholinesterase Inhibitors; CFB=Change from baseline.				

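### The tipping-point analysis reaches FAS members only, so treated subjects with no post-dose CDR-SB escape the plan's one MNAR check

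*Combined protocol and SAP*

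**What the plan says.** Section 8.2.7.1 plans three supportive analyses of the Week 130 CDR-SB result. One is a pattern-mixture tipping-point analysis, "which is intended to provide a measure of robustness" should more of the missing data than expected be missing not at random. Table 6 assigns it to the FAS.

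Under 8.2.4.1, FAS members must "have both 1) a baseline measurement for the analysis endpoint and 2) at least one within-analysis-window" post-dose observation. For the MFAS, "patients will only be required to have either 1) a baseline measurement for the analysis endpoint or 2) at least one within-analysis-window" observation. The same section adds: "The MFAS population will be utilized to conduct sensitivity analyses in this study for the primary endpoint". In Table 6 the MFAS appears only in the cLDA row, where missing data are handled by the model.

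In 8.2.7.5, steps a and b impute the missing values by treatment group, and step c subtracts c "from each of the imputed values of the active arms (to the detriment of active". The smallest c that brings p to 0.02495 or above is reported as the measure of robustness. The section then characterises the mechanism: "all missing data in the active arm are assumed to have a worse response", by c, than under MAR, while control-arm values stay as under MAR.

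**The concern.** A treated subject who left before any in-window post-dose CDR-SB has every post-baseline value missing, yet is not in the dataset that steps a to d work on. That subject's Week 130 value is never imputed and never receives c. A reader who takes the sentence in 8.2.7.5 at face value will think otherwise.

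The tipping-point analysis is the plan's only MNAR check on the primary efficacy endpoint. The MFAS/cLDA analysis does not fill the gap. It assumes MAR, and under MAR a subject with a baseline alone carries no direct information on post-baseline change. These subjects would affect the result mainly when c differs from zero, and that is where they are absent. The reported c would then suggest more robustness than the full set of treated subjects supports.

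**Working it through.** **Who is left out.** Section 8.2.7.1 uses all data from the initial trial, including from subjects who do not enter the extension. A subject with any in-window post-dose CDR-SB from that trial can therefore be in the FAS and is imputed at Week 130. The gap is narrower than extension non-entry: it concerns treated subjects with a baseline and no in-window post-dose CDR-SB at all.

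**Inputs.**
- 450 randomised per arm, with dropout of 25% at Week 104 and 37% at Week 130 (8.2.11.1.2, Table 9).
- Baseline SD 0.86, 30-month SD 3.05, mean change +2.13, correlation 0.359 (Table 8).
- Significance level 0.02495 (8.2.7.5).
- Share k of treated active-arm subjects with no in-window post-dose CDR-SB: not given, so assumed over a range.

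**The plan's figures.** No tipping value c is stated. The dropout figures are coherent: 1350 × 0.75 × 0.90 = 911, against the approximately 912 in the Trial Summary. The 37% is taken here as the missing share among treated subjects.

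**Formula.** Adding c to a share f of the active-arm Week 130 values moves the treatment difference by about f × c. If D is the distance from the c = 0 estimate to the significance boundary, the tipping value is about D / f. Over all treated subjects f = 0.37. Within the FAS the denominator shrinks by k while the observed share of 0.63 stays, so

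f(FAS) = 1 − 0.63 / (1 − k), and c(FAS) / c(all) ≈ 0.37 / f(FAS),

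taking D as much the same in both sets, since baseline-only subjects change a MAR estimate little.

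| assumed k | subjects per arm | f(FAS) | ratio of tipping c | simplified MI check |
|---|---|---|---|---|
| 1% | 4.5 | 36.4% | 1.02 | 1.01 |
| 2% | 9 | 35.7% | 1.04 | 1.02 |
| 5% | 22.5 | 33.7% | 1.10 | 1.11 |
| 8% | 36 | 31.5% | 1.17 | not run |
| 10% | 45 | 30.0% | 1.23 | 1.26 |

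For example, at k = 5%: 1 − 0.63/0.95 = 0.337, and 0.37/0.337 = 1.10.

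The MI check used 50 imputations, baseline and Week 130 only, a residual SD of 3.05 × √(1 − 0.359²) = 2.847, an illustrative observed difference of −0.85, the combining rules of 8.2.7.5, and 20 simulated data sets. c was added to the imputed active values.

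**Dependence on the 37%.** If 50% were missing at Week 130 (an assumption), the ratio is 0.50 / [1 − 0.50/(1 − k)] = 1.02, 1.06 and 1.10 for k = 2%, 5% and 8%. The inflation is smaller when more is missing overall.

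**Direction of the shift.** Table 8 shows decline on CDR-SB as a positive change, so subtracting c improves the active arm. In one simulated data set from the same illustration (k = 2%), literal subtraction moved the difference from −0.83 (p = 0.0012) at c = 0 to −1.19 (p = 0.000005) at c = 1. Followed as written, no positive c would tip a favourable result. The ratios above apply once c is added.

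**The case against.** The case for leaving the plan alone has five parts.

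- **The sentence is local to the analysis.** Table 6 names the FAS openly, and 8.2.7.5 says the aim is to test the primary approach, which uses the FAS. A reader might infer that the sentence is simply untrue. The documents do not support that: read within the FAS, it describes the intended mechanism. What stands is that its wording is broader than the analysis.
- **Stopping drug was not leaving the trial.** A reader might infer that intolerant active-arm subjects dropped out of the FAS early and in numbers. Section 5.8 says the initial trial used a retrieved-dropout approach, and 4.2.1.2 and 5.1.2 describe subjects who stopped treatment but kept their visits. Such subjects would have post-dose CDR-SB values. The documents give neither the count of the remainder nor any imbalance between arms. This stands, and may keep k low.
- **The size is assumed.** This also stands. At 1% to 2% the effect is a few percent, and it becomes material only from about 5%.
- **Little hangs on c.** There are no formal hypotheses, no threshold for c is set, and 8.2.11.1.2 allows for the case that "nominal marginal significance (ie, p-value < 0.02495) fails to be observed at Week 130". This limits the weight of the point, but the plan still offers c as its measure of robustness to missing data.
- **Moving the analysis to the MFAS would spoil the calibration.** c_prim matches the MI p-value to the FAS ANCOVA. A changed population would mix into that offset. This stands against replacing the FAS run, but not against adding a second one.

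**Conclusion.** The point holds in a limited form. Treated subjects with a baseline and no in-window post-dose CDR-SB receive no MNAR stress in any planned analysis, and the description in 8.2.7.5 claims more than is done. With the shift in the worsening direction, their exclusion raises the tipping c by about 4%, 10% or 17% if they make up 2%, 5% or 8% of the active arm. This assumes 37% missing at Week 130 and a MAR estimate that barely changes when they are added.

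A reader might conclude that the reported tipping point will be materially overstated. The documents do not establish that: the share is unknown, follow-up after stopping drug may make it small, and as step c is written the shift runs the wrong way for CDR-SB, so no favourable result would tip at all. That sign error is separate and has the larger effect.

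**What to change.** 1. Keep the FAS tipping-point analysis, calibrated to the primary ANCOVA as planned.
2. Add a second tipping-point row to Table 6 on MFAS subjects with a baseline CDR-SB. Impute all their post-baseline values in steps a and b, and apply the shift to those in the active arms. Take c_prim from the FAS run or report it separately.
3. In step c, state that for CDR-SB the constant is added, because higher scores are worse.
4. Report by arm the number of treated subjects with no post-dose CDR-SB, so that a reader can judge whether the second run matters.
5. Limit the sentence on missing active-arm data in 8.2.7.5 to the population analysed.

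The cost is one extra sensitivity run, one count table and small text edits. The second run may give a less favourable tipping point.
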